5.1 Study Visits

Perform study procedures as referenced in the Schedule of Study Assessments and Procedures (see protocol synopsis) in the order specified below.

5.1.1 *Screening*

- Informed consent
- Medical/ophthalmic and concomitant medication history, with review of inclusion/exclusion criteria
- BCVA
- Biomicroscopy
- Goldmann tonometry
- Gonioscopy
- Pachymetry
- Visual field testing
- Dilated ophthalmoscopy
- At any time during the visit after informed consent:
 - Heart rate/blood pressure
 - ECG
 - Physical examination
 - Phlebotomy and urine sample for clinical laboratories

5.1.2 *Day 0/Baseline*

- Medical/ophthalmic and concomitant medication history, with review of inclusion/exclusion criteria
- BCVA
- Biomicroscopy at all required timepoints
- Pupillary diameter
- Conjunctival hyperemia grading
- Goldmann tonometry at all required timepoints

- Phlebotomy for pK (any time prior to IP dosing)
- IP administration

5.1.3 *Days 1 and 4*

- Concomitant medications
- Adverse events
- IP compliance (Day 4 only)
- BCVA
- Biomicroscopy
- Conjunctival hyperemia grading (Day 4 only)
- Goldmann tonometry
- IP administration

5.1.4 *Days 14 and 28*

- Phlebotomy and urine sample for clinical laboratories (Day 28 only at any time during the visit)
- Concomitant medications
- Adverse events
- IP compliance
- Heart rate/blood pressure at all required timepoints
- BCVA
- Biomicroscopy at all required timepoints
- Pupillary diameter (Day 28 only)
- Conjunctival hyperemia grading at all required timepoints
- Goldmann tonometry
- Phlebotomy for pK at all required timepoints (Day 28 only)
- IP administration (Day 14 AM and PM, Day 28 AM only)
- Dilated ophthalmoscopy after final Goldmann tonometry (Day 28 only) – may be performed on following day for scheduling convenience.

6 ASSESSMENT OF EFFICACY

6.1 Efficacy Parameters

Primary Efficacy Endpoints:

The primary efficacy measure will be the mean change in IOP from Baseline (Day 0) IOP (mmHg) for each group on Days 14 and 28 at each matched time point as compared to vehicle. IOP will be measured according to the Schedule of Assessments and Procedures Table.

Secondary efficacy endpoints:

1. The observed IOP, mean change from Baseline, and % change from Baseline IOP at each matched time point at each visit, and
2. The mean observed, mean change from Baseline and mean % change from Baseline for the mean diurnal IOP at each visit, and
3. The proportion of subjects reaching a target IOP (≤ 18 mmHg) at each time point and with the mean diurnal IOP for each visit. Each concentration will be compared to vehicle and the difference in means between treatment arms will be presented.

6.2 Method and Timing

The efficacy parameter for this study is IOP as measured by Goldman applanation tonometry and recorded on the CRF. The timing of the IOP measurements are based on preclinical IOP data that was observed both in NHP and rabbits. The time points of diurnal IOP measurements are based on the expected peak and trough of H-1337 efficacy, the timing and frequency of dosing of H-1337 during 24 hours, and the circadian IOP diurnal curve.

7 ASSESSMENT OF SAFETY

7.1 Adverse Event Reporting

The investigator is responsible for monitoring the safety of subjects who have entered the study. Subjects should be asked at each visit about any changes in their health status. Any changes in health status after informed consent has been obtained, but prior to the first dose of IP, will be reported as medical history. AEs will be reported after the subject receives the first dose of IP (Day 0). Ongoing AEs at early termination or study completion (Day 28) will be followed until the event resolves, stabilizes, or for 30 days, whichever comes first.

All adverse events (serious and non-serious) must be documented regardless of the causal relationship to the study medication. The severity, frequency, seriousness, duration, relationship to IP(s), treatment of event, action taken with IP, and outcome for every adverse event should be documented in the source documents and CRFs.

Non-clinically significant incremental < 2 grade changes in conjunctival hyperemia (according to the photographic reference scale provided for the trial) are not required to be reported as adverse events.

To capture the most potentially relevant safety information during a clinical study, it is important that investigators record accurate AE terms on CRFs. Wherever possible, a specific disease or syndrome rather than individual associated signs and symptoms should be identified by the investigator and recorded on the CRF. However, if an observed or reported sign or symptom is not considered a component of a specific disease or syndrome by the investigator, it should be recorded as a separate AE on the CRF.

Investigators are required to report to Allysta Pharmaceuticals, Inc. or its representative all observed and/or volunteered AEs occurring during the clinical trial (21 CFR §312.64[b]) regardless of treatment group or suspected causality to the investigational drug.

7.2 Definition of Adverse Event

An AE is any unfavorable medical occurrence in a subject or clinical investigation subject administered a pharmaceutical product, which does not necessarily have to have a causal relationship with this treatment. An AE can, therefore, be any unfavorable and unintended sign, symptom, or disease temporally associated with the use of a medicinal (investigational) product, whether or not considered related to the medicinal (investigational) product. All AEs, including observed or volunteered problems, complaints, or symptoms, must be recorded. This definition also includes AEs which are reported up to 30 days after a subject has completed a clinical study. Therapeutic failures during clinical trials are not considered to be AEs.

Examples of adverse events include, but are not limited to:

- Abnormal test finding
- Clinically significant symptoms and signs

- Changes in physical examination findings
- Hypersensitivity
- Progression/worsening of underlying disease
- Change in BCVA > 10 letters
- Clinically significant change in pachymetry

Additionally, they may include the signs and symptoms resulting from:

- Drug overdose
- Drug withdrawal
- Drug abuse
- Drug misuse
- Drug interactions
- Exposure in utero (i.e., pregnancy within 30 days of study completion)

7.3 Abnormal Test Findings

The criteria for determining whether an abnormal objective test finding should be reported as an adverse event are as follows:

- Test result is associated with accompanying symptoms
and/or
- Test result requires additional diagnostic testing or medical/surgical intervention
and/or
- Test result leads to a change in study dosing or discontinuation from the study, significant additional concomitant drug treatment, or other therapy
and/or
- Test result is considered to be an adverse event by the investigator or Allysta Pharmaceuticals, Inc.

Reporting an abnormal test, in absence of any of the above conditions, does not constitute an adverse event. Any abnormal test result that is determined to be an error or is felt to be not clinically significant (NCS) by the investigator does not require reporting as an adverse event.

Abnormal laboratory test results reported to the investigator from the time the subject has taken at least one dose of the study treatment through last subject visit should be recorded as an adverse event if the above criteria are met.

7.4 Definitions of Non-Serious Adverse Events

Adverse events that do not meet the definitions for serious adverse events (SAEs) are non-serious AEs. Subjects should be instructed to report any AE that they experience to the investigator.

7.5 Definition of Serious Adverse Event

An SAE is any experience that suggests a significant hazard, contraindication, side effect, or precaution. This includes any experience that:

- Results in death
- Is acutely life-threatening
- Requires in-subject hospitalization or prolongs the existing hospitalization
- Results in persistent or significant disability/incapacity
- Is a congenital anomaly/birth defect
- Requires medical or surgical intervention to prevent one of the outcomes listed above

Examples of such medical events include allergic bronchospasm requiring intensive treatment in an emergency room or at home, blood dyscrasias or convulsions that do not result in in-subject hospitalization, or the development of drug dependency or drug abuse. This definition includes concurrent illness or injuries, exacerbation of pre-existing conditions and AEs occurring as a result of drug withdrawal, abuse or overdose. Serious adverse events observed during all periods of a clinical study are to be recorded, including those occurring during a period without study medication and whether or not the AE is judged to be related to the study medication.

7.6 Hospitalization

Reported adverse events associated with hospitalization or prolonged hospitalizations are considered serious. Any initial admission (even if less than 24 hours) to a healthcare facility meets these criteria. Admission also includes transfer within the hospital to an acute/intensive care facility.

Hospitalization does not include the following:

- Rehabilitation facility
- Hospice facility

- Respite care (caregiver relief)
- Skilled nursing facility
- Nursing homes
- Routine emergency admission
- Same day surgeries

Hospitalization or prolongation in the absence of a precipitating, clinical adverse event (e.g., for work-up of persistent pre-treatment lab abnormality) is not in itself a serious adverse event.

Diagnostic and therapeutic noninvasive procedures, such as surgery, should not be reported as adverse events. However, the medical condition for which the procedure was performed should be reported if it meets the definition of an adverse event. For example, an acute appendicitis that begins during the adverse event reporting period should be reported as an adverse event and the resulting surgical intervention should be recorded as a treatment of that adverse event.

7.7 Pregnancy

If a subject becomes pregnant during the study or up until 30 days after the last dose of IP, the Investigator must notify Allysta Pharmaceuticals, Inc. or its representative immediately and within 24 hours of learning of its occurrence by completing a Pregnancy Report Form and forwarding to Allysta Pharmaceuticals, Inc. or its representative. The pregnancy should be followed up to determine outcome, including spontaneous or voluntary termination, details of the birth, and the presence or absence of any birth defects, congenital abnormalities, or maternal and/or newborn complications. Any complications during pregnancy should be recorded as an AE and may constitute an SAE if they fulfill any of the specified criteria for an SAE. If upon outcome, the pregnancy meets one of the serious criteria (e.g. spontaneous miscarriage, congenital anomaly, or birth defect), it will then be considered an SAE and full details will be requested. These events will not be included in the clinical study report, but will be maintained in the clinical study files.

7.8 Definition of Unexpected Adverse Events

An AE is considered an unexpected AE if it is not mentioned in the Investigator's Brochure (IB), or if it is of greater frequency and/or severity than that mentioned in the IB, in the judgment of the Medical Monitor.

7.9 Definition of Relationship of Adverse Event to IP

The investigator's assessment of causality must be provided for all adverse events (serious and non-serious). The investigator must record the relationship in the CRF, as appropriate, and report such an assessment in accordance with the serious AE reporting requirements, if

applicable. An investigator's causality assessment is the determination of whether there exists a reasonable possibility that the investigational product caused or contributed to the adverse event. If the investigator does not know whether or not the investigational product caused the event, then the event will be handled as "related to investigational product" for reporting purposes, as defined by Allysta Pharmaceuticals, Inc. If the investigator's causality assessment is "unknown but not related to investigational product," this should be clearly documented in study records.

In addition, if the investigator determines a serious adverse event is associated with study procedures, the investigator must record this causal relationship in the source documents and CRF, as appropriate, and report such an assessment in accordance with the serious adverse event reporting requirements, if applicable. The categories are as follows:

0=Unrelated:	No temporal association, or the cause of the event has been identified, or the drug, biological, or device cannot be implicated.
1=Possibly Related:	Temporal association, but other etiologies are likely to be the cause; however, involvement of the drug, biological, or device cannot be excluded.
2=Probably Related:	Temporal association, other etiologies are possible, but unlikely.
3=Definitely Related:	Temporal association and no other etiologies possible.

7.10 Documentation of Severity of Adverse Events to IP

All adverse events will be examined to determine severity. The categories are as follows:

Mild:	Awareness of sign, symptom, or event, but easily tolerated. Does not interfere with subject's usual function.
Moderate:	Discomfort enough to cause some interference with usual activity and may warrant intervention.
Severe:	Incapacitating with inability to do usual activities or significantly affects clinical status, and warrants intervention.
Life-threatening:	Immediate risk of death.

7.11 Reporting Serious Adverse Events

SAEs (this refers to any AE that meets one or more of the aforementioned serious criteria) occurring after the subject receives the first dose of IP (Day 0) will be reported to Allysta Pharmaceuticals or its representative, followed until the event resolves or stabilizes, the subject's early termination or study completion (Day 28), or within 30 days of the last administration of IP, whichever comes first.

SAEs, and all deaths occurring within the study population, whether considered to be drug-related or not, will be reported on the SAE Report Form within 24 hours of knowledge of the occurrence to Allysta Pharmaceuticals, Inc. or its representative.

This can be done by emailing a completed SAE Report Form to:

Name: [name]
Title: Drug Safety Specialist Consultant
Company: Safety Sphere, LLC (www.safety-sphere.com)
Email: [contact]
Office [contact]
Office [contact]

Where the initial report is made verbally or by telephone to Allysta Pharmaceuticals, Inc. or the study monitor, the SAE Report Form must be emailed within 24 hours according to the instructions above.

The investigator will be requested to supply detailed information regarding the event at the time of the initial contact. All SAEs (initial and follow-up information) must be reported to the reviewing Institutional Review Board/Ethics Committee, according to their reporting requirements, and a copy of that report must be forwarded to Allysta Pharmaceuticals, Inc. or its representative. Allysta Pharmaceuticals (or designee) will report all Suspected Unexpected Serious Adverse Reactions (SUSARs) to Regulatory Authorities within 7/15 days of receipt depending on reporting requirements.

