7.12 Serious Adverse Event Follow-Up

For all SAEs, the investigator must submit follow-up reports to Allysta Pharmaceuticals, Inc., regarding the subject's subsequent course until the SAE has subsided, or until the condition stabilizes (in the case of persistent impairment), the subject dies, or within 30 days of the last administration of IP, whichever comes first.

SAEs that come to the attention of the investigator within 30 days following early termination or Day 28 will be reported to Allysta Pharmaceuticals, Inc. or its representative within 24 hours of knowledge of the occurrence.

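### Protocol Sections 7.1, 7.11 and 7.12 give different end points for following serious adverse events; 7.11, read literally, stops at early termination or Day 28

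*Protocol*

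**What the plan says.** Three sections of the protocol say when follow-up of an adverse event ends.

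- Section 7.11 (Reporting Serious Adverse Events): an SAE is followed until it resolves or stabilises, "the subject's early termination or study completion (Day 28), or within 30 days of the last administration of IP, whichever comes first".
- Section 7.12 (Serious Adverse Event Follow-Up): the investigator must send follow-up reports for every SAE until it subsides or stabilises, "the subject dies, or within 30 days of the last administration of IP, whichever comes first". ET and Day 28 are not in this list. The next paragraph adds a reporting duty: "SAEs that come to the attention of the investigator within 30 days following early termination or Day 28 will be reported".
- Section 7.1 (Adverse Event Reporting): events still open at ET or Day 28 "will be followed until the event resolves, stabilizes, or for 30 days, whichever comes first". The sentence does not exclude serious events, and the same section covers both kinds: "All adverse events (serious and non-serious) must be documented regardless of the causal relationship to the study medication".

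Section 4.3 treats follow-up data as essential for any subject withdrawn because of an adverse event or abnormal laboratory result, and asks for every effort at safety follow-up. It gives no duration.

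**The concern.** Section 7.11 takes the earliest of its listed dates. One of those dates is ET or Day 28, so an SAE still open at the last visit would get no further follow-up. Under 7.1 a non-serious event open on the same day would be followed for up to 30 days more. Section 7.12, which deals specifically with SAE follow-up, disagrees with 7.11 about the same events.

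Safety is the primary objective (Section 2), the drug has not been given to humans before (Section 1.3), and there is no external data monitoring committee (Section 10). Section 12.4 lets the trial be suspended on the Medical Monitor's review of the severity or incidence of complications. With about 20 subjects per arm, each SAE will be read individually. How far its outcome is known should not depend on which section the site consulted.

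**Working it through.** The plan gives no numerical result to reproduce. The check compares the latest follow-up date that each section allows for an event that neither resolves nor stabilises.

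**Inputs**

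- Last dose in a completer: morning of the Day 28 visit (Schedule of Assessments; Section 5.1.4). Visit window ±2 days.
- ET visit: within 14 days of the last dose (Section 4.3). Write L for the day of last dose and d for the days from last dose to ET, so 0 ≤ d ≤ 14.
- First possible dose: Day 0.
- Assumption: the 30 days in 7.1 run from ET or Day 28, because the sentence concerns events ongoing at that point. The section does not state a start.

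**Rules for an unresolved event in a surviving subject**

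- 7.11: end = min(ET or Day 28, L + 30)
- 7.12: end = L + 30
- 7.1: end = (ET or Day 28) + 30

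**Step 1. Can the 30-day limit in 7.11 ever operate?**

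- Completer: min(28, 28 + 30) = min(28, 58) = Day 28.
- Early terminator: min(L + d, L + 30) = L + d, since d is at most 14.
- Subject who stops the drug but stays in the study, which Section 4.3 allows: the earliest L is Day 0, giving Day 30. The Day 28 visit falls no later than 28 + 2 = Day 30, so the 30-day limit is never the earlier date.

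Within the scheduled windows it never sets the end date. It could do so only if the closing visit were missed or badly late.

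**Step 2. End of follow-up by section**

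| Subject with an open event | 7.11 | 7.12 | 7.1 |
|---|---|---|---|
| Completer, L = 28 | Day 28 | 28 + 30 = Day 58 | 28 + 30 = Day 58 |
| Early terminator, calendar day | L + d | L + 30 | L + d + 30 |
| Early terminator, days after ET | 0 | 30 − d = 16 to 30 | 30 |

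If the closing visit moves within its window, the completer's three dates move together and the 30-day gap is unchanged.

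**Step 3. An example.** An SAE starting on Day 27 in a completer is followed for 28 − 27 = 1 day under 7.11 and for up to 58 − 27 = 31 days under 7.12 or 7.1.

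**Step 4. Sensitivity to the 7.1 clock.** If the 30 days in 7.1 ran from last dose, 7.1 would coincide with 7.12: Day 58 for a completer and 16 to 30 days after ET for an early terminator. The conflict between 7.11 and 7.12 does not depend on this assumption.

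**Step 5. A second mismatch.** With the clock taken from ET, 7.1 ends d days later than 7.12, that is 0 to 14 days later for an early terminator. So 7.12 and 7.1 do not fully agree with each other either.

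**Step 6. Fit with neighbouring text.** An SAE first learned of after Day 28 must be reported under 7.12, yet is already past the end of follow-up in 7.11. Section 7.2 also counts events reported up to 30 days after a subject completes.

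**The case against.** The best defence is that 7.11 should not be read alone. Its subject is reporting; 7.12 is the section on SAE follow-up, covers every SAE, and is worded as an obligation. Section 7.1 does not exclude serious events, and Section 4.3 presses for follow-up of subjects withdrawn for an adverse event. A careful site would therefore keep following the event. That stands, and it rules out three stronger readings.

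- A reader might infer that the protocol as a whole follows SAEs for less time than non-serious events. It does not. That result arises only where 7.11 is applied as written.
- A reader might infer that a site cannot comply with all three sections. Nothing in 7.11 forbids longer follow-up, so a site that follows to the latest of the three dates satisfies them all. The sections are inconsistent but not mutually exclusive.
- A reader might infer that outcomes are lost for subjects withdrawn because of an SAE. Sections 4.3 and 7.12 both point the other way, although 4.3 sets no duration.

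It is also fair to say that the capture of SAEs is not reduced, given the 30-day reporting duty in 7.12. SAP Section 7.5 tabulates and lists SAEs by occurrence and term, and adverse events by intensity and relationship; it plans no summary of SAE outcome or duration. What is exposed is the completeness of outcome information on open events, not the planned safety tables.

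None of this removes the conflict: 7.11 permits a site to stop where 7.12 says it must continue.

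**Conclusion.** This is an internal inconsistency, and the protocol is wrong as written. For an SAE open at study end, a site following 7.11 literally stops 30 days before 7.12 requires in a completer, and 16 to 30 days before in an early terminator. It also stops up to 30 days sooner than 7.1 would allow for a non-serious event. Sites working from 7.12 or 7.1 would continue, so SAE outcome follow-up could differ by site.

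The result assumes that each list means the earliest of its dates and that closing visits fall within their windows. The figures for 7.1 also assume that its 30 days start at ET or Day 28. This check does not say which end point is right.

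**What to change.** Reconcile Sections 7.1, 7.11 and 7.12 so that all three give the same end point for SAE follow-up, with one stated start for any count of days. State explicitly whether the sentence in 7.1 on ongoing events applies to SAEs. Check the agreed wording against the Section 4.3 statement on subjects withdrawn for an adverse event and against the 30-day reporting duty in 7.12. The sponsor and Medical Monitor choose the rule.

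The cost is a short wording amendment with its usual ethics committee approval and a note to sites. It adds no scheduled visits and changes no planned analysis.

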7.12 Serious Adverse Event Follow-Up

For all SAEs, the investigator must submit follow-up reports to Allysta Pharmaceuticals, Inc., regarding the subject's subsequent course until the SAE has subsided, or until the condition stabilizes (in the case of persistent impairment), the subject dies, or within 30 days of the last administration of IP, whichever comes first.

SAEs that come to the attention of the investigator within 30 days following early termination or Day 28 will be reported to Allysta Pharmaceuticals, Inc. or its representative within 24 hours of knowledge of the occurrence.

